#### 7.4.2.3 Interim analyses and data monitoring

No interim analysis is planned for this study.

#### 7.4.2.4 *Multicenter studies*

A small center is defined as the center which randomizes less than 8 subjects. Small centers will be pooled prior to analyses. First, centers will be sorted by country, number of randomized subjects (descending order) and center number (ascending order). Pooling will start with

Galderma R&D RD.06.SPR.18252 Page 19 of 25

combining the largest of the set of small centers with the smallest center within that country. If there is a further need to combine data (the size of the pooled centers includes less than 8 subjects), the next smallest center will be combined with the next largest of the small centers, until the criterion of a minimum of 8 subjects is met. The process will continue until all pooled centers have a minimum of 8 subjects within the country. Any remaining centers will be pooled with the last pooled center within the country. The pooled centers will be referred to as 'analysis centers' in the statistical analyses.

# 7.4.2.5 *Multiple comparison/multiplicity*

Control of type 1 error, the experiment-wise error rate is controlled at alpha level of 0.05.

No adjustment for multiplicity is required for the primary efficacy endpoint as the statistical significance needs to be met for all 3 co-primary endpoints.

The statistical inferential testing for the secondary primary efficacy endpoint is conditional on the statistical significance of the primary efficacy endpoint, and all 3 co-secondary efficacy endpoints are required to reach statistical significance for the secondary efficacy endpoint to be statistically significant.

Therefore, no adjustment for multiplicity is required in this study.

## 7.4.2.6 Use of an efficacy subset of patients

The ITTT population is potentially a subset of the ITT population with moderate truncal acne at the Baseline visit. In practice, this excludes from the ITT population the children between 9 and 11 years old who did not meet inclusion criterion #4 (PGA) or #5 (Truncal lesion counts) at study entry (i.e. who do not have PGA of 3, at least 20 inflammatory lesions on the trunk and at least 20 non-inflammatory lesions on the trunk).

The PP/PPT Population will be determined prior to breaking the study blind using the criteria described in Section 5.5.

#### 7.4.2.7 *Active-Control studies intended to show equivalence*

Not applicable.

#### 7.4.2.8 Examination of Subgroups

All subgroup analyses are exploratory in nature.

To determine whether the treatment effect is consistent across various subgroups, the estimate of the between-treatment effect (with a nominal 95% CI) for the primary efficacy endpoint will be estimated and plotted within each category of the following classification variables:

- Age Group (<18 years, >=18 years)
- Gender (female, male)

Galderma R&D RD.06.SPR.18252 Page 20 of 25

- Race (white, non-white)
- Country (US, EU, Russia)
- Skin Phototype (I-III, IV-VI)

Treatment effects and nominal 95% confidence intervals by category for the classification variables listed above will be reported as well as presented graphically. Formal statistical testing of these interactions will not be performed.

For success rate on IGA, treatment effects and the nominal 95% confidence intervals will be summarized by category for the subgroup variable using the same method as the primary analysis.

For the change in lesion counts by type, treatment effects and the nominal 95% confidence intervals will be summarized by category for the subgroup variable using two-sample t-test.

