## 2 STUDY DESIGN

This is a Phase 3, multi-center, randomized, double blind, vehicle controlled study comparing CD5789 cream applied once daily in the evening versus its vehicle.

Group 1: CD5789 50µg/g cream applied once daily

Group 2: Vehicle Cream applied once daily

This Phase 3 study is designed to evaluate the efficacy and safety of CD5789  $50\mu g/g$  in subjects with moderate acne vulgaris on the face and moderate acne vulgaris on the trunk. Subjects with an IGA of 3 and a minimum of 20 inflammatory lesions and 25 non-inflammatory lesion counts on the face and a PGA of 3 and a minimum of 20 inflammatory lesions and 20 non-inflammatory lesion but no more than 100 non-inflammatory lesion counts on the trunk will be enrolled in the study.

Subjects will be treated once daily for 12 weeks and evaluated at Baseline, Weeks 1, 2, 4, 8 and 12/Early Termination.

Specific requirements for children between 9 and 11 years old who do not have moderate acne on the trunk at Baseline (i.e. who do not have PGA of 3, at least 20 inflammatory lesions on the trunk and at least 20 non-inflammatory lesions on the trunk):

In this case, it is up to the investigators to decide if these 9 to 11 years old subjects should be treated or not for truncal acne. In these subjects, treatment can be started (based on investigator's decision) even if e.g. PGA=1, or the subject has less than 20 inflammatory lesions on the trunk and/or less than 20 non-inflammatory lesions on the trunk). These subjects will not be assessed for efficacy, but they will be assessed for safety and local tolerability. A total of approximately 1200 subjects from USA (approximately 40%), EU and Russia (approximately 60%) will be randomized to the study stratified by center using a 1:1 ratio, to have 600 subjects per treatment arm randomized.

Subjects will be randomized to study treatments in a 1:1 ratio within a block for CD5789 cream and Vehicle cream, respectively. Randomization will be stratified by clinical trial centers using the Interactive Response Technology (IRT) System.

The kit number, a unique number corresponding to the number on the label of the study medication, will be assigned to each eligible subject at Baseline.

Galderma R&D RD.06.SPR.18252 Page 6 of 25

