# 6 SAMPLE SIZE CONSIDERATION

The assumptions used to power this study are based on the Phase 2 study (SPR.18223) on the Non-Japanese population. Success rates based on IGA are assumed 23% (CD5789) and 15% (Vehicle). For a 90% power to detect a significant difference versus vehicle using a two-sided test at a type I error of 0.05, 504 subjects per arm are needed for analysis.

Based on the results from statum 1 in the phase 2 study (SPR18223), the mean difference between the active and vehicle is estimated at 3 inflammatory lesions and 6 non-inflammatory lesions. Standard deviation of changes in lesion counts, based on phase 2 and on large phases 3 trials from other projects are estimated at 12 for inflammatory lesions and 20 for non-inflammatory lesions. Using these as assumptions and a sample of 504 evaluable subjects per arm, power is 95% at least for both lesion types.

Galderma R&D RD.06.SPR.18252 Page 12 of 25

To compensate for drop-outs and non-evaluable subjects (estimated at 16%), a total of 1200 subjects are to be randomized into each treatment group in a 1:1 ratio stratified by center, with 600 subjects in each treatment group randomized.

The assumptions for truncal acne being the same as for facial acne in terms of efficacy, therefore it is estimated that the power for truncal acne is adequate.

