#### Statistical method

• IGA Success Rate:

Success rate at Week 12 based on the IGA will be analyzed using the Cochran Mantel Haenszel (CMH) test stratified by analysis center (see definition in Section 7.4.2.4). The primary analysis will be performed using the overall ITT population based on the Multiple Imputation methodology (MI) as the primary imputation method for missing values, see Section 7.4.2.2.

The p-value for the treatment comparison will be generated from the general association statistic of the stratified CMH test. Difference in success rate between treatment groups (CD5789 50  $\mu$ g/g – Vehicle) and the 95% confidence interval of the difference will be based on the large sample approximation method for binary data. The success rate for each treatment group will also be displayed for the overall ITT population.

The treatment-by-analysis center interaction for success rate will be assessed for the overall ITT population by using the pair-wise Breslow-Day tests for homogeneity of the odds ratio across analysis centers at Week 12 at alpha level of 0.10. The consistency of the treatment effect across analysis centers will be evaluated using descriptive statistics and using graphical methods.

Facial Lesion Counts:

Changes from baseline in facial lesion counts at Week 12 will be analyzed separately by type (inflammatory and non-inflammatory) using an ANCOVA (Analysis of Covariance) model including baseline count, analysis center, and treatment as factors. The primary analysis will be performed using the overall ITT population using the primary imputation method for missing values.

The p-value for the treatment comparison, estimate of the LSMEANS treatment difference (CD5789 50  $\mu$ g/g – Vehicle), and the 95% confidence interval of the LSMEANS difference will be generated from the ANCOVA model.

The treatment-by-analysis centers and the treatment-by-baseline lesion counts interactions for Change in Lesions Counts will be assessed separately by the interaction term at Week 12 at alpha level of 0.10 for the overall ITT population. The consistency of the treatment effect across

Galderma R&D RD.06.SPR.18252 Page 16 of 25

analysis centers will be evaluated using descriptive statistics and using graphical methods. The consistency of the treatment effect by baseline lesion counts will be evaluated using graphical methods.

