# 7.4.2.1 *Adjustment for covariates*

The analysis of change from baseline in lesion counts will use an adjustment for the number of baseline lesions as described in Section 7.4.1.1.

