#### 6.7. Efficacy Figures

Figures will be presented for IGA and PGA success rate by visit using observed data. The week 12 success rate using the same MAR multiple imputation method as used in the primary analysis will also be graphed.

Figures will also be presented for the success rate at week 12 for each subgroup using MAR multiple imputation.

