#### 6.8. Efficacy Subgroup Analysis

The subgroup analyses will repeat the analysis of the three co-primary and co-secondary endpoints on all subgroups. The MAR multiple imputation method will be used to handle missing data.

For lesion count subgroup analysis, the t-tests will be done assuming unequal variances using Satterthwaite's formula for variance.

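### Optional improvement: exploratory lesion-count subgroup effects use an unadjusted t-test; adding the baseline count from the primary ANCOVA would narrow the intervals if baseline and change are correlated

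*SAP*

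**What the plan says.** SAP 7.4.2.8 makes all subgroup analyses exploratory. Their aim is to see whether the treatment effect is consistent across categories, using estimates with nominal 95% intervals and no interaction tests. IGA success is analysed by the primary method within each category. For change in lesion counts, effects and intervals "will be summarized by category for the subgroup variable using two-sample t-test".

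The clarification document attached to the SAP (final 23 October 2017, here called the addendum) supersedes the SAP wherever the two differ. Its section 6.8 extends the subgroup work to the co-secondary truncal endpoints and keeps the simpler test: "For lesion count subgroup analysis, the t-tests will be done assuming unequal variances using Satterthwaite's formula for variance".

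The primary lesion-count analysis in SAP 7.4.1.1 is an ANCOVA "model including baseline count, analysis center, and treatment as factors". SAP 7.4.2.1 adds, without exempting subgroups, that the analysis of change in lesion counts "will use an adjustment for the number of baseline lesions as described in Section 7.4.1.1". Addendum 2.5 also applies the primary and secondary efficacy analyses, and so the adjusted model for lesion counts, to three subpopulations of the ITT population.

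**The concern.** The same outcome is adjusted for baseline in the whole population and in the addendum's three subpopulations, but not in the subgroup categories. No reason is given. IGA success keeps its primary method in subgroups; only lesion counts move to a simpler one.

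The stake is precision. With no interaction tests, the intervals are the only stated evidence on consistency, so their width determines what a reader can conclude. Randomization is stratified by center only (SAP section 2), so baseline counts can differ by chance between arms within an age, gender or race category. An unadjusted comparison does not correct for that.

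Comparability is a smaller matter. Categories can be compared with one another because they share one method. Only a comparison of a category with the overall LSMEANS difference sets an unadjusted estimate beside an adjusted one.

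**Working it through.** **The plan's own figures.** The sample-size figures in SAP section 6 reproduce. Success rates of 23% versus 15% at 90% power and two-sided 0.05 give 504 per arm (pooled variance, no continuity correction). At 504 per arm, power is 97.8% for a difference of 3 with SD 12, and 99.7% for 6 with SD 20, against a stated minimum of 95%. Then 504 / (1 − 0.16) = 600. None of this is disputed or changed by the point.

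**Inputs.**
- SDs of change: SAP section 6 says they "are estimated at 12 for inflammatory lesions and 20 for non-inflammatory lesions".
- A large category: SAP section 2 says "A total of approximately 1200 subjects from USA (approximately 40%), EU and Russia (approximately 60%) will be randomized". The US share is 1200 × 0.40 / 2 = 240 per arm.
- A small category: 30 per arm, assumed.
- r, the within-arm correlation of baseline count with change: not in the documents, so assumed at 0, 0.3 and 0.5. Change contains baseline, so r is exactly 0 only if the regression slope of the Week 12 count on baseline is exactly 1.

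**Formulas for the 95% half-width, n per arm.**
- t-test: t(0.975, 2n−2) × SD × √(2/n)
- ANCOVA with baseline: t(0.975, 2n−3) × SD × √(1−r²) × √(2/n) × √(1 + 1/(2n−4))

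In large samples the ratio of t-test to ANCOVA width is 1/√(1−r²), which is 1.00, 1.05 and 1.15 at r = 0, 0.3 and 0.5.

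For SD 12 and n = 240, the t-test gives 1.965 × 12 × √(2/240) = 2.15. The ANCOVA at r = 0.5 gives about 2.152 × 0.866 × 1.001 = 1.87.

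| Case | t-test | ANCOVA r = 0 | r = 0.3 | r = 0.5 |
|---|---|---|---|---|
| SD 12, 240 per arm | 2.15 | 2.15 | 2.06 | 1.87 |
| SD 20, 240 per arm | 3.59 | 3.59 | 3.43 | 3.11 |
| SD 12, 30 per arm | 6.20 | 6.26 | 5.97 | 5.42 |

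In the first row the gain is 0, 0.10 and 0.29 lesions. The equivalent gain in sample size is 1/(1−r²): about 10% at r = 0.3 and 33% at r = 0.5. At 30 per arm and r = 0 there is a loss of about 1%.

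**With missing data.** A simulation used SD 12, a true difference of 3 and 16% of Week 12 values missing. The rate is from SAP section 6; missingness completely at random is assumed. Fifty imputations were drawn by linear regression on treatment and baseline within the category and pooled by Rubin's rules. The unequal-variance t-test was compared with an ANCOVA with treatment-specific residual variances.

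| Per arm | t-test, r = 0 / 0.3 / 0.5 | ANCOVA, r = 0 / 0.3 / 0.5 |
|---|---|---|
| 240 | 2.36 / 2.34 / 2.31 | 2.36 / 2.25 / 2.05 |
| 30 | 6.88 / 6.82 / 6.73 | 6.92 / 6.60 / 6.01 |

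Coverage was 94.6% to 95.4% for the t-test and 94.3% to 95.5% for the ANCOVA. Mean estimates were within 0.1 lesion of the true value at 30 per arm and within 0.03 at 240. A repeat with a common-variance ANCOVA showed the same pattern; its widths at 30 per arm were about 2% to 3% lower.

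**The case against.** The strongest reply is that this is a preference. The t-test is valid, the subgroups are exploratory, no decision depends on the interval widths, and the addendum revisited the method and kept it. All of that is true, and it is why the point is optional.

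Second, the gain cannot be established because r is not given. At 240 per arm and SD 12 the half-width falls only to 2.14 at r = 0.1 and 2.11 at r = 0.2, against an assumed effect of 3 lesions. At an assumed 10 per arm, adjustment widens it from 11.27 to 11.44 even at r = 0.2. This stands. In categories that small, neither method says much about a 3-lesion difference.

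Third, the 240 comes from Country, which is in SAP 7.4.2.8 but not in addendum 2.4. It therefore serves only as an example of a large category. Addendum 6.7 says "Figures will also be presented for the success rate at week 12 for each subgroup using MAR multiple imputation" and names no lesion-count subgroup figures, so the benefit may reach tables only.

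Fourth, the simulation is simpler than the planned imputation, which also uses earlier visits and is not specified by subgroup. Its absolute widths should not be read as this trial's. The closed-form ratio does not depend on it.

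Fifth, the change is more than a change of wording. Addendum 2.4 lists 17 categories for lesion counts; with 4 lesion endpoints and 50 imputations that is 17 × 4 × 50 = 3,400 fits. A common linear baseline slope is assumed, and leaving out center requires a second overall estimate. These are real but minor costs.

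**Conclusion.** The point holds as an optional, low-cost improvement and not as an error. The lesion-count subgroup analysis omits a covariate that is already collected and already used for the same outcome. In large categories its intervals are about 0%, 5% or 15% wider than necessary at |r| = 0, 0.3 or 0.5. These values of r are assumptions, so a gain near nil cannot be excluded, and a slight loss is possible in very small categories if r is near 0. Validity, the primary test, type I error and sample size are untouched. If the sponsor keeps the t-test, only precision is lost, including the correction of chance baseline imbalance within a category.

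**What to change.** In SAP 7.4.2.8 and addendum 6.8, replace the t-test by an ANCOVA within each category on treatment and the baseline count of the same lesion type and site (face or trunk).

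- State in advance that analysis center is omitted in every category.
- Keep the unequal-variance provision as treatment-specific residual variances with Satterthwaite degrees of freedom.
- Pool the adjusted difference and its 95% interval over the imputations with MIANALYZE. Write down the complete-data degrees of freedom used, and a rule for a fit that does not converge.
- Where subgroup results appear beside the overall result, give an overall estimate from this same model, labelled as such. The ANCOVA with analysis center remains the primary result.

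The cost is a few sentences in the two documents and one modified program run over the categories of addendum 2.4. No new data are needed. The price is one degree of freedom, the common-slope assumption and a second labelled overall estimate.

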#### 7.5 Safety analysis

All safety analyses are descriptive, and no formal inferential testing will be performed.

## 7.5.1 Extent of exposure

### 7.5.1.1 Study Duration

Study duration (day) is defined as the date of the last visit minus the date of the Baseline visit plus one. Study duration will be summarized by descriptive statistics using the ITT population.

#### 7.5.1.2 Treatment Duration

Treatment duration (day) is defined as "the date of the last application on face or the trunk, whichever is later, minus the date of the first application on face or the trunk, whichever is earlier, plus one".

Treatment duration will be summarized by descriptive statistics using the SAF population.

#### 7.5.1.3 Study Medication Usage (number of applications)

The study medication usage will be based on data collected on the CRF in terms of the number of applications applied.

Number of applications applied is calculated as the expected number of applications minus the total number of missed doses/applications during the treatment. If the number of missed doses/applications is unknown, then 50% doses will be assumed to be missed between two adjacent visits.

The expected number of applications is defined as the planned total number of applications during the exposed period.

Galderma R&D RD.06.SPR.18252 Page 21 of 25

Number of applications applied and the daily average applications applied will be summarized by treatment group for the SAF population.

In addition, study medication usage may also be summarized for the face using SAF population and for the trunk using the SAFT population separately.

## 7.5.2 Adverse events

A treatment-emergent adverse event (TEAE) is defined as an adverse event that occurred on or after the first study drug application.

The frequency (N %) of each adverse experience in the trial will be presented by system organ class and preferred term by treatment group using the SAF population.

Adverse events will be coded using the MedDRA dictionary

Overall summary of TEAEs [frequency (N, %)] will be provide for each treatment group. Additional summaries by System Organ Class (SOC) and Preferred Term (PT) will also be provided, along with TEAEs of special interest, serious TEAEs (SAEs), TEAEs related to the study drug, and TEAEs leading to discontinuation and severe TEAEs.

Subgroup analyses by Age Group (<18 years, >=18 years), Race (white, non-white), Gender (female, male), Country (Russia, EU, US) and Skin Phototype (I-III, IV-VI) will be provided.

All AE summary tables are based on the number and percentage of subjects who have experienced TEAE(s). For a given TEAE, a subject will be counted once even if he or she has experienced multiple episodes for that particular TEAE.

#### 7.5.3 Cutaneous safety

Only local tolerability (erythema, scaling, dryness, stinging/burning) worsened from baseline will be analyzed.

Analyses of the local tolerability on the face will be based on the SAF population; and the analyses of the local tolerability on the trunk will be based on the SAFT population.

Number and percent of subjects with worsened local tolerability from baseline will be presented for each treatment group by the severity scale for each of the assessments (erythema, scaling, dryness, stinging/burning) by visit.

Number and percent of subjects with worst local tolerability worsened from baseline during treatment period will also be presented for each treatment group by the severity scale for each of the assessments (erythema, scaling, dryness, stinging/burning). The same will be presented for the final local tolerability worsened from baseline during the treatment period.

Summary statistics by treating the severity scale as continuous outcome will also be presented.

Galderma R&D RD.06.SPR.18252 Page 22 of 25

Subgroup analyses by Age Group (<18 years, >=18 years), Race (white, non-white), Gender (female, male), Country (Russia, EU, US) and Skin Phototype (I-III, IV-VI) will be provided.

#### 7.5.4 Laboratory parameters

A summary table of the categorical grade shift changes using the normal ranges from baseline to Week 12/ET will be presented for each treatment group by each laboratory category parameter using the SAF population.

Only subjects with both baseline and Week 12/ET assessments will be included in this analysis.

#### 7.6 Other analyses

For the other variables, only observed data will be summarized without imputation for missing data. These data will be analyzed using the same methodology as described in Section 7.4.1.3.

The Dermatology Life Quality Index (DLQI, designed for use in adults, i.e. subjects over the age 16 years old) and Children's Dermatology Life Quality Index (C-DLQI, designed for use in children, i.e. subjects from age 5 to age 16) will be summarized descriptively.

Only SAF subjects who have both baseline and Week 12/ET assessments using the same ageappropriate questionnaire at both visits will be included in the analyses.

Total Scores and Change from Baseline at Week 12/ET for DLQI/C-DLQI, DLQI only, and C-DLQI only will be summarized.

In addition, number and percent of subjects will be reported by treatment group for each of the following categories of the effect of disease on the quality of life as specified in Table 2:

Table 2 DLQI/C-DLQI Categories				
DLQI		C-DLQI		
DLQI Category	Range of Total Score	C-DLQI Category	Score Maximum	
No effect	0 - 1	No effect	0 - 1	
Small effect	2 - 5	Small effect	2 - 6	
Moderate effect	6 - 10	Moderate effect	7 – 12	
Very large effect	11 – 20	Very large effect	13 – 18	
Extremely large effect	21 - 30	Extremely large effect	19 - 30	

Summaries of DLQI only and C-DLQI only by each dimension as defined in Table 3 below will also be provided.

Galderma R&D RD.06.SPR.18252 Page 23 of 25

Table 3 DLQI/C-DLQI Dimensions				
DLQI		C-DLQI		
DLQI dimensions	Score Maximum	C-DLQI dimensions	Score Maximum	
Total Score	30	Total Score	30	
Symptoms and feelings	6	Symptoms and feelings	6	
Daily Activities	6	Sleep	3	
Leisure	6	Leisure	9	
Work and School	3	School or holidays	3	
Personal relationships	6	Personal relationships	6	
Treatment	3	Treatment	3	

